6.1.11. Handling of Dropouts or Missing Data

6.1.11.1. Unknown or Unconfirmed Last Study Dose Date

If the end date of the medication intake is unknown or ‘unconfirmed’ (including but not limited to, eg, subject is lost to follow-up), it will be imputed as the earlier date of the disposition date (ie, date of the last contact with subject) and 7 days from the date of the last medication kit dispensed if the last contact visit is either V1E (OL baseline), or V2E (Week 2), and 14 days from the date of the last medication kit dispensed if the last contact visit is V3E (Week 4) or after.

6.1.11.2. Composite Score

Unless otherwise specified, any individual missing item in any scale won’t be imputed. When calculating a total score, subscale score, composite score, or any assessment with more than one item (e.g. EDE-Q modified global score and 3 subscale scores, SDS total score and subscale scores, MADRS total score, HAM-A total score, CSSA total score, DESS total score), if one or more items are missing at a visit, then the associated score (ie, total score or subscale score) will be set to missing.

Since a vendor generates for the SF-12, two component scores and subdomain scores using standard software, missing data is imputed by default algorithm provided by the vendor, which is provided on [Attachment 9.2](#).

For analyses of the change from baseline for a given effectiveness parameter, only subjects who have both baseline and at least one post-baseline measurement are included.

6.1.11.3. Incomplete/Missing Dates

6.1.11.3.1. Start/End Dates for Adverse Event

Treatment-emergent adverse events (TEAEs) are those reported adverse events with an onset date on or after the first day of the open-label treatment period (See [Section 6.1.1.1](#) for definition of the OL treatment period), through 7 days after study drug discontinuation (14 days for serious adverse events and deaths).

A conservative approach will be used to handle the missing dates for AE onset date and end date to identify the treatment-emergent AE (ie, if the available incomplete date cannot determine treatment emergent status, the AE will be considered as a treatment-emergent AE). No imputation is to be done to calculate AE duration.

6.1.11.3.2. Start/End Dates for Prior/Concomitant Medication

Partial dates of non-study medication start/end date need to be imputed in order to classify the medications as prior or concomitant medications, or post-treatment medication (ie, medication initiated after the last dose of study medication). A conservative approach will be used to handle the incomplete date(s) for medication start/end date (ie, if the available incomplete date(s) cannot determine the concomitant relationship relative to the open-label treatment phase, the medication is considered as a concomitant medication).

6.1.12. Subgroup Analysis

For a limited number of descriptive analyses, data will be presented for analysis group by subgroup below as needed:

- Age group at OL Baseline (years): “< 40 years”, “≥ 40 years”
- Gender: Male, Female
- Race: White, Non-white
- BMI at OL Baseline: Non-obese (ie, Normal & Overweight), Obese class I/II, Obese class III

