Breath Alcohol Test		Х		X			X	
12-Lead Electrocardiogram (ECG)				X	X	X	X	

Table 2: Schedule of Assessments (Continued)

Abbreviations: BSN = baseline; EOS = End of Study; EOT = End of Treatment; OL = open label; V = visit

^a Week 12 in core study. Baseline assessments indicated as "carried over" are primarily performed as part of Week 12 visit in the core study and do not need to be repeated; the data will be duplicated from Week 12 visit or other visits (such as for height) in the core study.

^b Subjects who discontinue from the study prior to completion of treatment with study drug will be asked to return to the site and complete the EOT assessments within 1 day of discontinuation and complete the Withdrawal Period visits and calls.

^c Subjects will take the first dose of study drug in this study on Day 1 (the morning following the baseline visit); there will be no break in study drug treatment between the core study and this extension study. All study drug will be administered by the subject once a day at approximately the same time each morning including on the days when clinic visits occur.

^d At the approximate midpoint between the scheduled monthly treatment period visits (ie, 14 ± 2 days after a visit), the site staff will contact the subject via telephone, text, or email to monitor for SAEs, AEs, and concomitant medications, as well as to remind subjects about adherence to study drug administration and upcoming visits, following which an unscheduled visit may be scheduled, if necessary.

Footnotes continued on the next page.

- ^e Informed consent will be obtained from all subjects after all procedures from the core study have been completed and before any study procedures unique to this study are performed.
- ^f Subjects must be fasting for at least 8 hours (may have water) prior to the indicated laboratory tests. Visits should be scheduled in the morning.
- ^g The "Since Last Visit" version will be used. Subjects who answer "yes" to "suicidal ideation" item 4 (active suicidal ideation with some intent to act, without specific plan) or item 5 (active suicidal ideation with specific plan and intent) on the C-SSRS assessment at any time during the study must be referred to the Investigator for follow up evaluation.
- ^h The Structured Interview Guide for the HAM-A (SIGH-A) will be used for the administration of the HAM-A.
- ⁱ The Structured Interview Guide for the MADRS (SIGMA) will be used for the administration of the MADRS.

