15.3.2. Definitions of Assessments

The following definitions will be used for assessments:

- Double-blind (DB) Baseline (ie, Baseline assessment of the double-blind study [core study]): the last assessment made on or before double-blind randomization as described in the core protocols;
- OL Baseline (ie, Endpoint assessment of the double-blind treatment period of core study) or Baseline assessment of the open-label study (SEP360-322): the last assessment made during the double-blind treatment period, as described in the core protocols;
- Week 52 Endpoint/Withdrawal Baseline: the last post-OL Baseline assessment made prior to or at Week 52 visit.
- Withdrawal Endpoint: the last post-Withdrawal Baseline assessment made prior to or at Week 55 visit.

Continuous variables will be summarized using descriptive statistics (N, mean, standard deviation [SD], median, range, 95% confidence interval [CI] as needed). Where changes are reported, the reference will be to "DB Baseline". Where relevant, changes from "OL Baseline" will also be reported.

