6.1.3.2. OL Baseline

Except for height (for all subjects), demographics (for all subjects) and EDE-Q modified (for subjects continued from SEP360-221), unless otherwise specified, based on the protocol of SEP360-322 and the schedule of assessment ([Attachment 9.1](#)), OL Baseline values are to be carried over from W12/Endpoint in the core studies. The OL Baseline is defined as the last assessment made on or before Day 1 of the extension study (ie, Baseline assessment in the open-label study [SEP 360-322] for demographic (for all subjects) and EDE-Q modified (for subjects from SEP360-221), and height at the screening and the Endpoint assessment of the double-blind studies [SEP 360-221, or SEP 360-321] (for all subjects), otherwise).

As indicated in the protocol, height at the screening visit in the core studies will be carried over as OL Baseline. For operation convenience, the protocol specified that data collected at the EOT visit of the core studies are recorded in core studies only and are not to be saved in the clinical database of the extension study. Height at OL Baseline visit will be assigned a value per the corresponding Study Data Tabulation Model (SDTM) dataset of core studies directly.

Unless otherwise specified, at each study visit of study SEP 360-322, data derivation rule and missing imputation method for aggregated parameters that involves multiple individual items (eg, total score, subscale score, or composite score), are same as the corresponding ones in individual core study SAPs. DB Baseline is defined same as the Baseline in individual core study per core study SAPs. DB Baseline used in the analysis of study SEP 360-322 will be extracted from corresponding Analysis Data Model datasets (ADaM) of the core studies directly.

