6.1.9. Analysis Group and Analysis Subgroup

For all subjects in Study 360-322, summary tables, wherever applicable, will be presented by analysis group per subject’s previous participation in core studies (ie, subjects previously randomized to dasotraline, subjects previously randomized to placebo, all subjects combined) as described as below

- Pbo-Das: Subjects previously randomized to placebo in studies SEP360-221 or SEP360-321
- Das-Das: Subjects previously randomized to dasotraline group in studies SEP360-221 or SEP360-321
- All-Das: all subjects combined

For subjects continued from Study SEP360-221, analyses per selected data may be conducted as needed; summary of these analyses will be presented per subject’s previous participation in study SEP360-221 as described below (hereafter, referred as ‘Analysis Subgroup A’):

- Pbo-Das: previously randomized to placebo
- Das-Das: previously randomized to dasotraline 4–8 mg/day
- 221-Das: all subjects continued from study SEP360-221

For subjects continued from Study SEP360-321, analyses per selected data may be conducted as needed; summary of these analyses will be presented per subject’s previous participation in study SEP360-321 as described below (hereafter, referred as ‘Analysis Subgroup B’):

- Pbo-Das: previously randomized to placebo
- Das4-Das: previously randomized to dasotraline 4 mg/day
- Das6-Das: previously randomized to dasotraline 6 mg/day
- AllDas-Das: previously randomized to dasotraline (4 mg/day or 6 mg/day)

322

- 321-Das: subjects continued from study SEP360-321

Subjects in Study SEP360-322 may be further grouped and presented according to their predominant dose (alternatively, modal dose, see [Section 6.1.10](#)) and the maximum dose during the open-label treatment period as below, as needed. Hereafter, analysis subgroup based on the modal dose will be referred as ‘Analysis Subgroup C’ and analysis subgroup based on the maximum dose will be referred as ‘Analysis Subgroup D’.

Analysis Subgroup C

- Das4: subjects with modal dose of dasotraline 4 mg/day
- Das6: subjects with modal dose of dasotraline 6 mg/day
- Das8: subjects with modal dose of dasotraline 8 mg/day
- All Das: all subjects combined

Analysis Subgroup D

- Das4: subjects with maximum dose of dasotraline 4 mg/day
- Das6: subjects with maximum dose of dasotraline 6 mg/day
- Das8: subjects with maximum dose of dasotraline 8 mg/day
- All Das: all subjects combined

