- AEs by SOC and PT, Serious AEs by SOC and PT, and AEs leading to discontinuation by SOC and PT (sorted alphabetically by SOC and PT within SOC).
- AEs by PT, AEs with special interest by PT (sorted by descending order per frequency count)

Exposure categories to be summarized are given below:

- Exposure categories : 1-13 days, 14-27 days, 28-83 days, 84-167 days, \geq 168 days.

AEs by Subgroup

The TEAEs will be summarized by SOC, PT for subgroups (see [Section 6.1.12](#)) below:

322

- Age group at OL Baseline (years): < 40 years, ≥ 40 years
- Gender: Male, Female
- Race: White, Non-white
- BMI at OL Baseline: Non-obese , Obese class I/II, Obese class III

Discontinuation-Emergent Adverse Event (DEAE) (ie, AEs Onset After Last Study Dose)

All summary of DEAEs will be based on a ‘modified’ withdrawal population (see [Section 6.1.8](#)), which includes all subjects in the withdrawal population plus the subjects who do not enter withdrawal period, but their last study dose dates are at least 2 days earlier than their last study visit (ie, Week 52/EOT visit). The rationale of defining ‘modified’ withdrawal population is that the AE information after the last study dose is expected to be continuously collected till the last study visit

The overall incidence of DEAEs and serious DEAEs will be summarized by analysis group. The DEAEs also will be summarized by SOC and PT, and by PT of each analysis group.

In addition, incidence of DEAEs by SOC and PT will be also summarized using time intervals beginning with the earliest AE concurrent withdrawal duration in the withdrawal period, where denominators in percentage calculation for withdrawal duration intervals (in days) will be based on the number of subjects whose withdrawal duration are no less than the first day of the interval. Withdrawal duration (in days) will be derived as the last withdrawal visit date minus the last dose date +1 and withdrawal duration categories to be assessed are 1-7 days, 8-14 days, and ≥ 15 days.

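### The adverse-event subgroups by BMI are cut on OL Baseline BMI, which is an on-drug value for Das-Das and a pre-drug value for Pbo-Das, so the same BMI row describes different kinds of subject in the two columns

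*SAP*

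**What the plan says.** **Subgroup cut.** SAP 6.1.12 lists BMI among the subgroup factors as "BMI at OL Baseline: Non-obese (ie, Normal & Overweight), Obese class I/II, Obese class III". SAP 7.4.2 repeats it ("BMI at OL Baseline: Non-obese , Obese class I/II, Obese class III") under the only table that the SAP text names for these subgroups: "The TEAEs will be summarized by SOC, PT for subgroups". The subgroup tables are split by column: "data will be presented for analysis group by subgroup below as needed". No subgroup on DB Baseline BMI is planned.

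**What OL Baseline is.** SAP 6.1.3.2 says that, with a few exceptions, "OL Baseline values are to be carried over from W12/Endpoint in the core studies". Weight is not one of the exceptions. Footnote c of the schedule of assessments (Protocol Table 2) adds that "there will be no break in study drug treatment between the core study and this extension study". SAP 6.1.1.1 already treats the visit differently in the two groups: the open-label treatment period starts at the OL Baseline visit for subjects who had dasotraline in the core study, and on Day 1 for those who had placebo.

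**What the drug does to weight.** Protocol 4.2 and 4.3 report dose-dependent weight loss in earlier studies, without a size.

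**References for change.** Protocol 15.3.2 and SAP 7.4.1 make DB Baseline the default ("Where changes are reported, the reference will be to" DB Baseline) and add changes from OL Baseline where relevant. SAP 6.1.9 gives Pbo-Das and Das-Das their own columns, beside "All-Das: all subjects combined".

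**The concern.** A subgroup factor should describe subjects before the treatment whose effects the table is meant to show. Here it does so for Pbo-Das only. In the Das-Das column the Non-obese row combines subjects who were not obese before dasotraline with subjects who left the obese classes while taking it. The second kind have, by selection, responded strongly on weight and tolerated the drug for 12 weeks, so they may have a different adverse-event profile. In the Pbo-Das column any such movement happened without the drug. A reader who compares the Non-obese row across columns, or reads down the BMI rows within Das-Das, cannot separate an effect of body size from sorting by drug response.

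A related and smaller issue affects the pooled column. The All-Das change from OL Baseline averages change since starting dasotraline (Pbo-Das) with change after 12 weeks of it (Das-Das). It falls short of the change since starting the drug wherever part of the effect is already present at core Week 12.

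**Working it through.** The plan states no figure on this point, so there is none to reproduce. Two illustrations follow.

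**1. Movement between BMI classes in Das-Das by OL Baseline**

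From the documents:
- Three classes with cuts at 30 and 40 kg/m² (SAP 6.1.12 with Table 9.3).
- Height fixed at core Screening (SAP 6.1.13), so a given percentage weight change is the same percentage BMI change.

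Assumed, because the documents do not give them:
- Pre-drug BMI normal with mean 33 and SD 6, or mean 36 and SD 7, dropping values below 18.5.
- Percentage loss over 12 weeks normal, independent of starting BMI, with mean 0 to 7% and SD 4 or 4.5.

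Formula: OL BMI = DB BMI × (1 − loss/100); compare class before and after. Each range below covers both BMI settings and both SDs (2,000,000 draws per setting).

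| Mean loss | Fall to a lower class | Rise to a higher class | Share of OL Non-obese row that was obese at DB Baseline |
|---|---|---|---|
| 0% | 5.0–5.8% | 4.8–5.6% | 10–13% |
| 2% | 8.7–9.6% | 2.4–3.0% | 16–19% |
| 3% | 11.0–11.9% | 1.6–2.1% | 20–23% |
| 5% | 16.1–17.3% | 0.6–0.9% | 26–30% |
| 7% | 21.8–23.3% | 0.2–0.4% | 33–37% |

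Pairing mean 33 with SD 7 and mean 36 with SD 6 widens the downward range at 2–7% loss to 8–24%. With no mean change and an SD of 2.5, about 3% move each way.

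The 0% row is ordinary variation, which Pbo-Das would also show if placebo weight did not shift. The downward excess over that row is about 4 points at 2% loss (for example 9.2 − 5.6 = 3.6) and about 16 to 18 points at 7% (22.0 − 5.6 = 16.4; 23.1 − 5.1 = 18.0).

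In subjects: if the core arms were of equal size (1:1 and 1:1:1, assumed) and completed equally, the Das-Das share is (150 + 320)/780 = 60%, or about 300 of the projected 500. Then 9 to 23% is about 27 to 69 subjects.

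**2. All-Das change from each reference**

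Let L be the full on-drug change, w the Das-Das share and f the fraction of L reached by core Week 12. Assume no change on placebo and the same final effect in both groups.

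- From OL Baseline: Pbo-Das shows L and Das-Das shows L(1 − f), so All-Das shows (1 − w)L + wL(1 − f) = L(1 − wf).
- From DB Baseline: both groups show L, so All-Das shows L.

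The values of w (0.50 to 0.67) and f (0.3 to 0.8) are assumed:
- w = 0.50, f = 0.3: 1 − 0.15 = 0.85 of L
- w = 0.60, f = 0.5: 1 − 0.30 = 0.70 of L
- w = 0.67, f = 0.8: 1 − 0.536 = 0.46 of L

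For an assumed L of −8% in weight, the pooled OL Baseline cell would read −6.8% to −3.7%, against −8% from DB Baseline. If placebo subjects changed by p over the core study, the DB Baseline cell becomes L + (1 − w)p, which is off by about 0.4p at w = 0.60.

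**The case against.** **BMI at extension entry is a legitimate descriptor.** TEAEs are counted from the start of the open-label period, and OL Baseline BMI describes who enters it, as does age, which is cut at the same visit. This stands as a reason to keep the OL Baseline cut as a supplement. It does not make that cut comparable between columns: three months does not change age through the drug, but it can change BMI.

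**The tables are few and descriptive.** The SAP limits them to a small number, as needed, by analysis group, and SAP 6.2.2 and 7.4.1 rule out hypotheses and inferential safety analyses. This stands and bounds the consequence. In a study without inference, though, the descriptive tables are the result.

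**The size is assumed.** This stands. The documents support the direction only, and part of the 9 to 23% is ordinary movement. No effect on any adverse-event rate has been computed.

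**The pooled column.** A reader might infer that All-Das is the main safety column and that no planned output gives change since starting dasotraline. The documents do not support this. DB Baseline is the default reference and is pre-drug for both groups. Changes from both baselines are planned for laboratory, ECG, vital-sign, weight and effectiveness data, and Table 7 lists QTc increases from each. Das-Das from DB Baseline and Pbo-Das from OL Baseline together supply change since first dasotraline by group. Nothing in either document gives All-Das priority over the separate columns.

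**Conclusion.** The point holds for the BMI subgroups. By the SAP's own definitions the cutting variable is post-exposure in Das-Das and pre-exposure in Pbo-Das, the drug is described as acting on it, and no pre-drug alternative is planned. Under the stated assumptions about 9 to 23% of Das-Das subjects sit in a lower class than before treatment, and 0.2 to 3% in a higher one, against about 5 to 6% each way with no mean change. The direction rests on the protocol's qualitative statement about weight loss; the size rests wholly on assumed BMI, weight-loss and variability figures.

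For the pooled column only the narrow form holds: the All-Das change from OL Baseline mixes two kinds of reference and, under the assumptions used, shows 46 to 85% of the full on-drug change. The default DB Baseline cell does not share this, apart from the placebo-period term.

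It would go too far to say that the plan biases a tested effect, or that adverse-event patterns by BMI will appear or vanish. Nothing is tested, and no such pattern has been shown. The consequence is limited interpretability of the subgroup safety tables.

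**What to change.** 1. In SAP 6.1.12 and 7.4.2, define the BMI subgroups on DB Baseline BMI. If a description by BMI at extension entry is wanted, keep the OL Baseline cut as a labelled supplementary table, with a note that it is an on-drug value for Das-Das.
2. Footnote the All-Das cell for changes from OL Baseline as mixing drug-naive and on-drug references, or omit it. Direct readers to All-Das change from DB Baseline, which is already the default.
3. A combined pre-dasotraline baseline (DB for Das-Das, OL for Pbo-Das) is optional. Its drawback is that each All-Das visit would pool unequal exposure: at Week 52, about 64 weeks on drug for Das-Das (12 + 52) and 52 for Pbo-Das.

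The cost is small: SAP wording and, if both cuts are shown, one extra set of tables. SAP 6.1.3.2 already takes DB Baseline from the core analysis datasets, and SAP 7.4.5.1 already plans BMI-category shifts from DB Baseline. The one trade-off is that DB Baseline BMI is 12 weeks older than extension entry for Pbo-Das, so it describes those subjects slightly less well at the point where they first take dasotraline.

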6.1.13. BMI (kg/m²)

BMI is calculated at each visit using the following formula:

$$\text{BMI} = \text{weight (kg)} / (\text{height(m)} * \text{height(m)})$$

Height is per measurement at Screening visit in core studies.

6.1.14. EDE-QM Items 4, 5, and 6

EDE-QM items 4, 5, and 6 are expected to collect numeric type of data. Due to the data fields were set as character type in clinical database, total 11 records (6 cases for item 4, 3 cases for item 5, and 2 cases for item 6), which were collected at early stage of the study, had a range type of data (ie, 1-2, 8-10 etc.) instead of a single integer value. For such cases, the higher value (ie, the worse value) are to be used in EDE-QM related summary analyses (eg, mean actual value and change from baseline). In addition, for a few records with character value of ‘NO’, ‘NONE’, ‘NA’, and ‘N/A’, zero will be used instead in terms of analysis purpose. The original data will be displayed in data listing.

322

6.2. Methods of Analysis

6.2.1 General Methodology

All statistical inference analyses will be performed with 2-sided tests at a significance level of 0.05, and 2-sided 95% confidence intervals (CI) will be calculated whenever appropriate. All data will be summarized by analysis group (or analysis subgroup) and visit as appropriate. All subject data will be presented in data listings by subject.

6.2.2 Statistical Hypotheses for Trial Objectives

Because of the nature of an open-labeled study, no hypotheses are planned and to be tested.

6.2.3 Interim Analysis

One interim analysis was planned to support regulatory filing of BED NDA submission and a separate SAP was developed for the interim analysis.

